## Clinical Research Plan

# Importance of the study

Head posture varies according to the physiologic and functional activity of the individual. Head postures are divided into 'active feeding position', 'head up position', and 'extended head position'. (1,2) The position in which the head extends 30° forward during feeding is known as the 'active feeding position'. (2) This posture causes the mandible and mandibular closure pathways to be positioned more anteriorly than normal. During drinking, the head extends 45° backwards and the mandible moves posteriorly. (3) Any change in head posture causes the muscles attached to the mandible to stretch and lengthen, resulting in a change in mandibular position. Changes in mandibular position result in changes in occlusal contact points and the occlusal forces generated at these points. The literature supports the relationship between head posture and occlusal contact points. (4,5)

Micron-sized changes in occlusal contacts can trigger severe dysfunction and pain in the temporomandibular joint (TMJ). Therefore, it is important to obtain accurate interocclusal records and to detect occlusal interferences. The interocclusal record is defined as a record of the positional relationships of opposing teeth and jaws. (6) Interocclusal records facilitate the assessment of occlusion for diagnostic or treatment planning purposes. Restorations with occlusal incompatibility produced using inaccurate interocclusal records result in increased adjustment time of the restoration or the need for restoration replacement. This is time-consuming and costly for both the clinician and the patient. Therefore, reliable interocclusal records obtained by providing appropriate occlusal records directly affect the success of prosthetic or indirect restorative procedures. (7)

With digitalization, the use of intraoral scanners has enabled dental impressions and interocclusal records to be obtained digitally. After the scanning of both dental arches is completed with intraoral scanners, the interocclusal record begins. Right and left interocclusal records are taken. After ensuring that the patient closes the teeth in the appropriate position, the intraoral scanner head is positioned to see the buccal surfaces of the teeth on the relevant side. The scanner is moved anteriorly starting from the most posterior tooth. The images captured during scanning are matched with the full arch scans through the software and the upper and lower jaw scans are brought to closure. The same process is repeated for the other side. Thus, the interocclusal registration is completed. Digital interocclusal records have the advantages of being obtained in a shorter time and in a more comfortable way for both clinician and patient, easy and error-free transfer to the laboratory, and the ability to obtain dynamic interocclusal records in addition to static occlusal records with various software. (8)

Iwauchi et al. compared the accuracy of digital and conventional interocclusal records in a clinical study. Eight subjects with natural dentition and no missing teeth were included in the study. Two different intraoral scanners and silicone-based impression materials were used to take dental arch impressions and interocclusal records in three groups. The plaster models obtained from silicone-based impressions were transferred to the articulator with the interocclusal records obtained with silicone-based material and the model was scanned with a laboratory scanner to acquire digital interocclusal records. These procedures were repeated four times for each group. The obtained interocclusal records were exported in "stl" format and the accuracy of the interocclusal records was evaluated by overlapping the measurements with each other. At the same time, the precision of the interocclusal recording methods was evaluated by overlapping each of the four repeat measurements. As a result of the study, digital interocclusal recordings were shown to be more accurate than the conventional method. (9)

In a clinical study, Fraile et al. compared the accuracy of digital interocclusal records obtained with three different devices. Twenty-five healthy volunteers were included in the study. In the control group, contact points were determined and photographed with eight  $\mu m$  thick articulating paper, which is considered the gold standard. Interocclusal records were obtained digitally by using an intraoral scanner, transferring the models obtained from conventional measurements to the articulator and scanning them with a laboratory scanner, and using the T-Scan III interocclusal analysis system. As a result of the study, intraoral scanners were shown to be reliable in determining interocclusal contact points compared to the gold standard. (10)

For a correct occlusion assessment, the condyle should be directed to the appropriate position in the TMJ. For this purpose, the spatial position of the maxilla relative to the skull base, intercondylar and condyle pathway

distance, hinge axis, static and dynamic relationship of the mandible should be determined and transferred to the articulator with facebow recording. Nowadays, digital facebow transfer is possible and the records obtained are transferred to the digital articulator, facilitating the workflow. Digital facebow includes a new digital occlusal analysis software that enables the recording of mandibular functional movements. In this method, occlusal contact patterns are captured during the actual movement of the mandible and analyzed for appropriate therapeutic positioning of the mandible or occlusal interferences. For this purpose, the digital scan records of both jaws are combined with the motion records obtained using a special attachment table and visualized as a single image. Since the TMJ motion pathways are also recorded, it is also possible to define the appropriate therapeutic position to relieve the TMJ with this software. This method provides a deeper and more comprehensive understanding of the relationship between the structure and function of the occlusion (11,12).

There are not enough studies in the literature to clinically evaluate the changes in occlusal contact points according to different head positions using digital methods. This study aims to quantitatively evaluate the changes in occlusal contact points with digital interocclusal and facebow recordings taken in three different head positions. The hypothesis of the study is that there is no statistically significant difference in interocclusal contact points in different head postures.

Research will be supported by the Scientific Research Projects Coordination Unit of the University of Hacettepe, and an agreement will be reached with the Faculty of Dental Medicine of the Hacetepe University (Hacettepe University Dental Faculty [name]), the research center, in order to reach a positive conclusion about the necessary board decisions. Support address: University of Hacettepe [name].

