# Sample size and strength analysis

This study uses the PS Version 3.0 package. =0,50,  $\alpha$ =0,05, test strength 1-=080, repetition correlation r=0,20 is the default, and the total sample size is determined to be at least 36. But because working with a larger sample reduces the level of misunderstanding, it is desirable to work with as many patients as possible.

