# **Primary Conclusion Point**

The comparison of the interocclusal records obtained is a quantitative evaluation of differences in interoclusal contacts in different head positions according to the appropriate head-bone-spine position.

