#### **Statistical Evaluation**

Data from all volunteers participating in the study will be included in the statistical analysis. First, the Kolmogorov Smirnov adaptation test and the Shapiro-Wilk test are considered to be used to see if the data has a normal distribution. Subsequently, the differences between groups will be assessed using parametric or non-parametric statistical methods, depending on the case. Previous studies will be studied in detail, and comparisons will be evaluated using appropriate tests. Taking into account previous studies, it is envisaged that independent and dependent group tests, Kruskal Wallis, or one-way variance analysis, will be used.

Any possible change in the clinical research plan or process will be promptly notified to the research center, relevant institutions, boards, and healthy volunteers. Derogations from the clinical research plan are monitored and managed by the research center, and inconsistencies with the plan are expressly prohibited.

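### The hypothesis is worded as a non-significant test result and only significance tests are named, so the analysis does not deliver the plan's aim of quantifying contact differences from the neutral head position

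*Combined protocol and SAP*

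**What the plan says.** All quotes are from the combined protocol and SAP.

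- **Importance of the study** gives the aim: "This study aims to quantitatively evaluate the changes in occlusal contact points with digital interocclusal and facebow recordings taken in three different head positions". The next sentence gives the hypothesis: "The hypothesis of the study is that there is no statistically significant difference in interocclusal contact points in different head postures". No alternative hypothesis follows.
- **Primary Conclusion Point** describes the endpoint as a "quantitative evaluation of differences in interoclusal contacts in different head positions", taken relative to the proper head and spine position. **Primary Data** also says that the contact differences will be quantified.
- **Statistical Evaluation** plans normality checks, after which "the differences between groups will be assessed using parametric or non-parametric statistical methods, depending on the case". On the tests themselves, "it is envisaged that independent and dependent group tests, Kruskal Wallis, or one-way variance analysis, will be used". The section names no effect estimate or confidence interval and does not say how a non-significant result will be reported.
- **Sample size and strength analysis** gives an unlabelled 0.50, alpha 0.05, power 0.80 (printed as "test strength 1-=080") and a repeat correlation of 0.20, and concludes that "the total sample size is determined to be at least 36".

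**The concern.** A hypothesis should concern the true contacts in the three positions. This one concerns the outcome of a test, which depends on the sample size and the noise as well as on the truth. It is presented as the hypothesis of the study, so a small or noisy data set would satisfy it.

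The analysis section does not correct for this. An omnibus test such as Kruskal-Wallis or one-way ANOVA gives one p value for three positions. It does not say how far flexion or extension moves the contacts from neutral, which is what the aim and endpoint ask for.

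The background section argues that micron-sized contact changes can cause joint dysfunction and pain. An unsupported message that posture makes no difference would therefore be the costly error. An interval shows which differences the data leave open; a p value alone does not.

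**Working it through.** **1. Does the named analysis deliver the endpoint?** The aim, Primary Data and Primary Conclusion Point all ask for the size of a difference, and the endpoint takes the proper head position as its reference. Statistical Evaluation names tests only. Paired tests could come under the dependent-group tests it mentions, but no contrast with neutral, estimator or interval is specified. The intention to quantify is stated; the method is not.

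**2. Inputs.** Sample size section: 0.50 (label missing), alpha 0.05, power 0.80, r = 0.20, n = 36. Assumptions: a two-sided test, one unadjusted paired comparison, equal SDs in the positions.

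**3. Can 36 be reproduced?**

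- *0.50 in SD-of-difference units.* Normal approximation: n = ((1.96 + 0.84)/0.50)², rounded up to 32. The noncentral t gives 34. This is close to 36, but does not use r.
- *0.50 in raw SD units, r = 0.20.* SD of the difference = √(2 × (1 − 0.20)) = √1.6 = 1.265, so the standardised difference is 0.50/1.265 = 0.395. The normal approximation gives 51 and the noncentral t gives 53. This does not reproduce 36.
- *0.50 as Cohen's f.* Repeated-measures ANOVA with three levels and r = 0.20 needs 12 people, which is 12 × 3 = 36 records.

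The documents do not settle which reading was meant, so the size has to be shown as a range.

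**4. Chance of a non-significant result at n = 36 when the 0.50 is true.** For the paired t-test the noncentrality is standardised difference × √36, on 35 degrees of freedom. For Cohen's f it is 36 × 3 × 0.50²/(1 − 0.20) = 33.75.

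| Reading of 0.50 | Noncentrality | Power | Missed |
|---|---|---|---|
| SD-of-difference units | 0.50 × 6 = 3.00 | 83.1% | about 17% |
| Raw SD units, r = 0.20 | 0.395 × 6 = 2.37 | 63.5% | about 36% |
| Cohen's f, repeated-measures ANOVA | 33.75 | over 99.9% | under 0.1% |

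**5. What a non-significant result leaves open.** The 95% half-width is t(0.975, 35) × SD of difference/√36, with t = 2.030.

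- SD-of-difference units: 2.030 × 1/6 = 0.34.
- Raw SD units: 2.030 × 1.265/6 = 0.43.

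Take an observed difference of 0.20, which is non-significant in both cases. The intervals are 0.20 ± 0.34 = −0.14 to 0.54, and 0.20 ± 0.43 = −0.23 to 0.63. Both include 0 and 0.50. The value 0.20 is illustrative. The same holds for any observed difference between 0.50 − 0.34 = 0.16 and 0.34 on the first scale, and between 0.50 − 0.43 = 0.07 and 0.43 on the second.

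**The case against.** The strongest reply is that the hypothesis sentence is an ordinary null, set up to be rejected and loosely phrased. The background says the literature supports a link between posture and contacts, so the investigators appear to expect an effect. The study is sized by power to detect something, which is a difference design. This stands as far as it goes: the sentence may well be a conventional null.

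Four stronger readings are tempting, and the documents do not support them.

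- *That the plan will treat non-significance as proof of no posture effect.* No section states such a rule. What can be said is that the wording allows it and nothing rules it out.
- *That the plan has no intention of quantifying differences.* Primary Data and Primary Conclusion Point both express it. What is missing is the estimate and interval that would carry it out.
- *That the study has a planned difference of 0.50 SD which it misses 36% of the time.* The label on 0.50 is missing, and the raw SD reading needs 53 volunteers, not 36. The nominal 20% miss is no defect either; it is the type II error chosen in any design with 80% power.
- *That an equivalence test is required.* Equivalence is not a stated objective, so its absence is not an error.

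It is also fair that 36 is a minimum and that the plan would like more volunteers; a larger sample would narrow the intervals. None of this supplies the missing estimate and interval.

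**Conclusion.** The point holds as a gap between the stated aim and the named analysis. The hypothesis is a test outcome that any p above 0.05 satisfies, and the analysis section names only tests, while the aim and primary endpoint call for quantified differences from the proper head position.

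The size depends on an assumption that the documents do not settle. For one unadjusted two-sided paired t-test at n = 36, a true 0.50 is missed about 17% of the time on the SD-of-difference reading and about 36% on the raw SD reading with r = 0.20. If 0.50 is Cohen's f, an effect of that size would almost never be missed in a repeated-measures ANOVA, although smaller effects still could be and no estimate would be planned. On the first two readings, a non-significant result can leave 0.50 open.

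This is an inexpensive improvement to analysis and reporting, not a flaw that undermines the design. The substantive change is to the primary report; rewording the null on its own would be clerical.

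**What to change.** 1. In Statistical Evaluation, make the primary report the two within-volunteer differences, flexion minus neutral and extension minus neutral, each with a 95% confidence interval. If a non-parametric analysis is used, report the paired Hodges-Lehmann estimate and its interval. Any overall test can be kept alongside.
2. In Importance of the study, state the null as equal true means (or medians) of the contact measure in the three positions, with the alternative that at least one differs.
3. Add one sentence: a non-significant result will be reported as a difference not shown, with its confidence interval, and not as absence of a posture effect.
4. In the sample size section, restore the label and units of the 0.50, so that the intervals can be read against it.

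The cost is a few sentences and standard software output. No extra data, volunteers or equivalence margin are needed.

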#### **Materials And Methods:**

The study will include healthy volunteers with natural dentition and no missing teeth. The study is planned to obtain a total of three different interocclusal records for three different head positions according to the appropriate head-neck-spine posture with an intraoral scanner, followed by digital facial arch recording and quantitative evaluation of changes in interocclusal contacts. No patient randomization was planned in the study, and direct digital interocclusal records and oJMA records were planned to be collected from each participant who met the inclusion criteria. Each volunteer who meets the inclusion criteria will be expected to carefully read the "Informed Consent Form" and then make his/her own decision about whether or not to participate in the study without any pressure. In line with the consent of the volunteer, surface scanning and digital dental arch records will be taken.

The intraoral scanner to be used in the study (TRIOS4; 3Shape A/S; Kopenhagen, Denmark) will perform surface scans of the mandibular arches and interocclusal records. TRIOS4 was chosen because all data to be acquired can be obtained without being subjected to laboratory stages that are prone to deformation, it offers a more comfortable and shorter procedure time for volunteers, it is manufactured following the latest technological developments, and it is a reliable and fast device with the support of literature knowledge. The device is manufactured in Denmark (3Sahep Trios A/S [name], [contact], [contact]) and its authorized representative in our country is BatiGroup Dental (BatiGroup Dental Dental Products Trade Anonim Şirketi, [name], [name], [contact]). The device is in pen form and the tip used in the mouth will be sterilized for each volunteer. Possible risks include a feeling of nausea that may occur during surface scanning in individuals with severe nausea reflex, but this can be seen during all dental procedures for individuals with nausea reflex and does not present a different risk.

Another device to be used in the study is an optic jaw motion analyzer system (zebris JMA Optic; zebris Medical GmbH, Germany) and the software program (zebris WINJAW+; zebris Medical GmbH, Germany). The sensitivity, accuracy and reliability of oJMA is supported by literature information, which has a higher data acquisition speed and can be easily integrated with digital surface scans, and at the same time shortens the procedure time for the clinician, patient and technician. The device is manufactured in Germany (Zebris Medical GMBH, [name], [contact], [contact]). The device consists of an electronic face-bow, mandibular sensor, C-bow positioning tip and pedal. All parts will be cleaned and sterilized under appropriate conditions after each

procedure. Due to the ultrasonic sensor content of the device, its use in individuals with pacemakers or defibrillators is considered risky and these individuals will not be included in the study. Exclusion criteria are clearly stated in it.

Investigational products have been manufactured in accordance with good manufacturing practices determined according to the relevant legislation. These products will be used in accordance with the approved research protocol. The control and calibration procedures of the devices to be used within the scope of the research will be carried out regularly. The data obtained will be stored in the software of the devices and will not be shared with third parties. Personal data will not be shared with anyone and will be kept only by the clinician. Data that do not contain personal data, which are shared with the dental laboratory after being created with the coding method, will be automatically deleted from the software used by the dental laboratory within a maximum of three months from the date of sharing. The records of the devices in the system will be deleted immediately after the completion of the work. Confidentiality assurance of the data will be realized with the form signed by the individuals. A comparative device will not be used in the study. In case of early termination or temporary suspension of the study for any reason, the volunteers included in the study will be immediately informed by the principal investigator. The principal investigator or a researcher to be assigned by the principal investigator will immediately notify the sponsor of all adverse events, serious adverse events, device defects. The volunteer experiencing an adverse event will be followed up at the research center until the effects disappear completely and regain their health, and necessary interventions will be made. Information on patient code, age, gender, inclusion and end date will be recorded on the case report form in order to ensure accurate patient follow-up. In case of any damage that may occur to the volunteers due to the research, the damage will be immediately notified to the sponsor and will be provided within the scope of the research. Digital interocclusal records and oJMA records, which are found to be useful within the scope of the research, can also be used in the future prosthetic dental treatment of the volunteers. The results of the study may be used in dental education or scientific publications without disclosing the personal information of the volunteer. If the volunteer signs the 'Informed Voluntary Consent Form', he/she consents to the right of access to the original medical records by monitors, examiners, the Ethics Committee, the Ministry and other relevant health authorities related to this research, but the information is under the assurance of complete confidentiality.

# **Digital Interocclusal Record Groups**

Group 1 (G1): Digital interocclusal recording taken in the neutral position with the head aligned in the head-neck-spine plane

Group 2 (G2): Digital interocclusal recording taken in the position where the head is positioned at 30° flexion relative to the head-neck-spine plane

Group 3 (G3): Digital interocclusal recording with the head positioned in 45° extension relative to the head-neck-spine plane

## oJMA Record

For each participant, the spatial position of the maxilla relative to the skull base, the condyle distance and the static and dynamic recording of the mandible will be taken in accordance with the digital occlusal analysis module in the oJMA.

All records will be completed in two sessions and carried out by a single operator. During the first session, participants will be scanned using the intraoral scanner (TRIOS4; 3Shape A/S; Copenhagen, Denmark) in accordance with the scanning protocol recommended by the manufacturer. Each of the scans will take 1.5 minutes and will be completed in a total of three minutes. A goniometer (Goniometer, 360°; Saehan, Germany) will be used to standardize the head position of participants before taking interocclusal records in the dental unit. (13,14) All participants will be in the dental unit, where the back of the unit will support the person's lumbar and thoracic vertebrae, with their arms freely sitting next to the body and watching directly in front of them. The neutral position of the head (G1, PN), 30° flexion (G2, PF), and 45° extension (G3, PB) will be determined by a goniometer. For each participant, the neutral position will first be determined, with the head, neck, and spine on the same axis, the fixed arm of the gonyometer standing on the ground, the central meatus acusticus externus, and the measuring arm aligned with the Camper plane. Then, for

each head position, the measuring arm shall be fixed to the base of the ala nares, with the head in the position of 30° flexion and 45° extension. Then, in addition to normal clinical procedures, these two head positions will take right and left direct digital interocclusal records. These records will take one minute for each main position, and inter-occlusal records will be completed in a total of three minutes. The closing movement will be repeated to get the participants to an intercuspal jaw position, and the muscles will get used to this position. Subsequently, participants will be asked to close their mandible in a repeated intercuspal position and they will be asked to maintain this position. The intraoral scanner will be placed between the teeth and the cheek with minimum pressure, without disturbing the closure, and will be recorded from the teeth's buccal surfaces with movement from the rear to the front. The TRIOS software will automatically match the same areas in the dental arch scans during the interocclusal record with the scan of the buccal surface of the teeth, closing the scans of the lower and upper jaws. Participants will repeat the same procedure for right and left interocclusal records without disturbing the intercuspal jaw position. The oJMA will be recorded at the second session and last 15 minutes. All recordings will then be integrated into the analytical module of the oJMA software (zebris WINJAW+; zebris Medical GmbH, Germany) in 'stl' format.

